Target number of participants	We anticipate to recruit 800 participants for this study over the course of 4 years

Criteria for evaluation	
Primary outcome measure(s): The primary outcome of the study is to evaluate if specific heritable arrhythmic disorders are associated with changes in selected protein distribution/expression levels at cell-cell junctions within the buccal mucosa. Our preliminary studies suggest that protein distribution/expression alterations in the buccal mucosa mirror equivalent changes that occur in the myocardium of patients with ACM. This study will evaluate the use of this "novel diagnostic tool" in individuals at risk of sudden cardiac death due to other, more common forms of arrhythmic disorders including the cardiac channelopathies. The processing approach (laboratory technique: immunocytochemistry) for protein distribution visualization has been optimized to be qualitative rather than quantitative. In this sense - each sample will be characterized by "presence" or "absence" of a specific protein at the cell-cell connections. We deem that the qualitative approach is not subject to bias and will ensure accuracy and reproducibility of the results.
 
Secondary outcome measure(s): A potential secondary outcome of the research is whether we can correlate protein distribution in the buccal mucosa with specific genotypes. Our preliminary results on the cohort of patients with ACM suggest that mutations in different genes result in different protein distribution patterns within the buccal mucosa. Being able to predict the gene bearing the disease-causing mutation will significantly reduce the time and cost of genetic sequencing. Identifying the specific gene underlying a heritable arrhythmic disorder is of pivotal importance as increasingly developing genotype/phenotype correlations help individualized risk identification and patient management.
 
Another potential secondary outcome of the research has to do with the effect changes in the patients' treatment plans may have on protein distribution. An example has to do with a protein known as Connexin43 (Cx43). Cx43 is the major gap junction protein expressed in the heart and is responsible for the electrical coupling of the cells and the smooth propagation of electricity throughout the myocardium. Cells at the buccal mucosa also express Cx43. It has been shown that patients with arrhythmic disorders show decreased distribution of Cx43 at the cell borders in their hearts and this "Cx43 remodeling" has been associated with an increased risk for arrhythmias. Our preliminary studies show that patients with ACM, as well as patients with different types of cardiomyopathy (including dilated, hypertrophic and ischemic) show Cx43 remodeling in their buccal mucosa. If a patient shows Cx43 remodeling during initial sampling and in a follow-up visit his clinical care team deems necessary to change his treatment plan (for instance, if he/she is to be started on a different anti-arrhythmic drug) we would like to study Cx43 distribution again during one of his/hers follow up visits. If the new treatment plan results in restoration of Cx43 at the buccal mucosa cell connections, and given how protein distribution in the buccal epithelium mirrors protein distribution in the heart, this finding may be an indication of successful arrhythmia management. It could thus, potentially, provide us with a non-invasive, straightforward and risk-free means to assess therapy efficacy in the future.

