an informed consent form, a copy of which they will get to keep. If the sampling is taking place at home, the patient needs to return the signed consent form to City St George's, University of London along with their samples. If seen on site, the patient will then provide a study team member with 6 buccal smear samples. These samples will be transferred to [name] laboratory at City St George's, University of London. If using the at-home kit, the patient will obtain the buccal smears himself and then mail them to SGUL. The samples will be identified by a study ID number. There shall be no personal or medical information noted on them. Once at [name] laboratory at City St George's, University of London, they will be subjected to immunohistochemical analysis to characterize specific protein distribution. [name] and her lab team members will be blinded to the patient information. There shall be a single copy of a file linking the study ID number to a specific patient, accessible only by the patients' regular medical care providers.

Patients participating in the protein expression sub-study will provide a study team member with buccal cell samples to be transferred to [name] laboratory at City St George's, University of London. Such samples can only be obtained on-site and not by the patients themselves at-home.

Intervention plan and rationale

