The data will be stored in TIF (images) format. The observations of the images will be logged on excel spreadsheets. City St George's, University of London is developing an institutional data repository as part of a Jisc-funded RDM Shared Service (April 2016 - September 2017). This will provide discoverability, secure storage and long-term preservation for all research data deposited in it. The PI will not have access to patient data/medical records. Slides will be labelled by a unique study participant ID code. There shall be no hard copy of the key linking the code to patients kept in the laboratory. There will be a linked document stored in the ISF JREOLOG0002. The study will be conducted in compliance with SOPs, GCP, all relevant laws of the EU and the UK including but not limited to: the Human Rights Act 1998, the Data Protection Act 1998, the Human Medicines Regulations 2012, ICH, the World Medical Association Declaration of Helsinki (2008), the NHS Research Governance Framework for Health and Social Care (2005). At the end of the study all coded samples shall be disposed of in accordance with the Human Tissue Authority's code of practice. Data generated will be kept on a password-protected workstation within a controlled-access office at City St George's, University of London. Computer softwares and firewall protection are up to date. City St George's, University of London servers are protected by line-interactive uninterruptible power supply (UPS) systems. No data will be kept in cloud-based storage. Only secure City St George's, University of London -controlled FTP servers will be used to share data with other team members. No sensitive data will be emailed according to ISO 27001. Digital data kept on City St George's, University of London servers are backed up overnight, every night, to hard disk and then cloned to tape storage. Full backups of all the data will be carried out monthly. The cloned tapes are stored separately in a fireproof and bombproof safe off-site. Laptops will be backed up and data removed from them as soon as practicable. This is in accordance with the City St George's, University of London Information Security and Removable Media policies: <https://portal.sgul.ac.uk/org/lis/computing-services/infosec-external>

Archiving arrangements

The trial essential documents along with the trial database will be archived in accordance with the sponsor SOP JREOSOP0016. The agreed archiving period for this trial will be 10 years.

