Statistical design

Statistical input in trial design

Endpoints

Primary endpoints

The primary end point will be the presence of signal for a specific protein at the junctions of the buccal smear sample. No quantification of immunoreactive signal will be performed as this approach may increase bias. Accordingly, the results for each protein stain will be categorized as “present” or “absent”.

The end point of the sub-study will be whether a protein of interest is expressed at control levels or significantly decreased levels in the presence of a mutation. Accordingly, the results for each protein examined will be categorized as ‘control’ or ‘reduced’.

Secondary endpoints

Not applicable for this study.

Sample size and recruitment

Sample size calculation

The sample size was calculated based on the size of the St. George's and satellite centres' Arrhythmia Services. The number selected constitutes only a fraction of the individuals evaluated and regularly followed at the hospitals involved and will allow us to obtain statistically significant results for each arrhythmic disorder.

Planned recruitment rate

Based on the number of patients/family members evaluated at the arrhythmic services at City St George's, University of London, we estimate that we shall be recruiting approximately 200 individuals per year over the 4 year course of the study.

Statistical analysis plan

Summary of baseline data and flow of patients

The participants will include individuals from 3 groups:

1. Patients already diagnosed with an arrhythmic disorder
2. Relatives of patients diagnosed with arrhythmic disorders to establish risk status
3. Relatives of SCD victims for risk stratification.

There shall be no randomization of the participants and no differential treatment amongst the population. All individuals enrolled will only provide a buccal smear sample.

Primary endpoint analysis

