- Research is not used to make decisions directly affecting individuals
- Short retention limits
- Restricted access controls
- Other (please specify)

Samples will be identified by a study ID number only. No personal data will be noted on the slides.

A key linking the study ID numbers to specific individuals will be kept in protected workstations at respective hospital sites only accessible by the participants' regular medical team.

How long will you need to hold the personal data for after the study has completed?

Not applicable

How will you make sure that you are holding data for the appropriate length of time and no longer?

Not applicable

How will the data be held /stored?

Personal data for all patients/family members are routinely held in medical files and electronically by the individuals' regular medical care providers. There shall not be shared with the principal investigator.

Will you be using any electronic and/or paper Case Report Forms (CRFs) to collect data? If so what are these and how will they be held securely and managed at the end of the project?

A data collection form, not including any personal data, will accompany each set of slides or cell suspension sample. This will include:

- The arrhythmia syndrome the participant has been diagnosed with

- Whether the participant has a family history of sudden cardiac death
- Whether the participant is taking any regular medication
- Whether the participant has been diagnosed with additional medical conditions
- Whether the participant is bearing a known disease-causing mutation
- The number of slides obtained (or if participating in the sub-study whether a single or double round of toothbrush rubbing was required to obtain sufficient cells)
- The team member obtaining the smears/cell sample (or the participant if using the at-home kit)

These will be completed by the participant's regular medical providers.

Following completion of the immunohistochemical/western immunoblotting analysis the principal investigator will complete the second part of the form with any changes observed in the distribution/expression levels of key proteins investigated.

There shall be no personal data noted on the form.

The forms will be held in [name] office at City St George's, University of London. The office is locked and accessible only by the PI.

Upon completion, they shall also be scanned and an electronic copy held in [name] St George's, University of London workstation accessible by the PI only.

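### The plan claims an unbiased, reproducible present/absent reading but never measures repeatability, and its laboratory blinding conflicts with the form that accompanies the slides

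*Combined protocol and SAP*

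**What the plan says.** The synopsis (Criteria for evaluation, primary outcome) describes the staining read-out as qualitative and adds: "We deem that the qualitative approach is not subject to bias and will ensure accuracy and reproducibility of the results". The Primary endpoints section (14.2.1) is more guarded. It says "No quantification of immunoreactive signal will be performed as this approach may increase bias", and that "the results for each protein stain will be categorized as" present or absent. The sub-study has its own endpoint, protein expression at control or reduced level, which is not at issue here.

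On blinding, Overall design (6.1) says of the laboratory head that she and "her lab team members will be blinded to the patient information". Slides carry a study ID only, and Data handling and analysis (12.4) denies the principal investigator access to medical records.

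The DPIA (section 25), in its answer on case report forms, says: "A data collection form, not including any personal data, will accompany each set of slides or cell suspension sample". Its listed contents include "The arrhythmia syndrome the participant has been diagnosed with", regular medication, additional conditions and any known disease-causing mutation. The care team fills in that part. After the laboratory analysis, "the principal investigator will complete the second part of the form with any changes observed in the distribution/expression levels of key proteins investigated". The forms are kept in an office that only the principal investigator can enter.

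On storage, section 12.4 says: "The data will be stored in TIF (images) format".

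**The concern.** Reducing an image to two classes does not remove reading error; a borderline image still has to go one way or the other. Whether the same image would get the same call again is an empirical question, and the plan asserts the answer instead of collecting it.

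Much rests on these calls: the pairwise Fisher comparisons between disorders, any sensitivity or specificity in the style of the pilot, the first-year decision on continuing channelopathy recruitment, and the before-and-after comparison of Cx43. An abnormal self-taken sample may also lead the care team to discuss an earlier appointment (Subsequent assessments, 10.4).

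Bias is a separate matter from repeatability. If the person making the call can see the diagnosis or mutation, accuracy could be overstated. The plan's protection against this is blinding, and two of its sections describe arrangements that do not fit together.

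**Working it through.** **Search for a measurement.** Laboratory procedures (10.5.1), the data sections (12.2 and 12.4) and the statistical sections (14.2 to the interim analysis) contain no second or repeat reading, no agreement statistic and no definition of absent. Primary endpoint analysis limits itself to frequencies and associations. The sensitivity-analysis entry only points back to the preceding text. The repeat samples in 10.4 are new smears with no planned test-retest analysis, so they do not check the reading of an image.

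**Blinding, side by side.** Section 6.1 blinds the laboratory to patient information. The DPIA sends diagnosis, medication and mutation status with the slides and has the reading entered on the same form. No step separates the two parts of the form before the call is made.

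**Plan's own figure.** Primary endpoint analysis gives 34 of 39 patients with arrhythmogenic cardiomyopathy (ACM) showing absent plakoglobin. 34/39 = 87.18%; the stated 87.1% is the truncated value. The exact 95% CI is 72.6% to 95.7%. The stated 100% specificity cannot be checked, because the number of non-ACM samples is not given.

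**Illustration of misreading.** Assumptions, none from the documents: calls flip at random at rate e in both directions, the pilot values are taken as error-free, and prevalence is 10% or 50%.

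- Observed sensitivity = 0.8718(1 − e) + 0.1282e
- Observed specificity = 1 − e
- PPV = p·Se / [p·Se + (1 − p)(1 − Sp)]
- Apparent change between two readings of an unchanged participant = 2e(1 − e), if errors are independent

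| e | Sensitivity | Specificity | PPV, p = 10% | PPV, p = 50% | Apparent change |
|---|---|---|---|---|---|
| 2% | 85.7% | 98% | 82.6% | 97.7% | 3.9% |
| 5% | 83.5% | 95% | 65.0% | 94.3% | 9.5% |
| 10% | 79.7% | 90% | 47.0% | 88.9% | 18.0% |

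Example, e = 5% and p = 10%: 0.1 × 0.8346 / (0.1 × 0.8346 + 0.9 × 0.05) = 0.0835/0.1285 = 65.0%.

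**Precision of a re-read.** 10% of the planned 800 is 80 participants. With one call each for a given protein, 76/80 = 95% agreement has an exact 95% CI of 87.7% to 98.6%. Under independent flips, agreement A corresponds to e = [1 − √(2A − 1)]/2. So 95% agreement means e of about 2.6%, and the interval runs from about 0.7% to 6.6%.

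**The case against.** The plan is not without protection. Laboratory blinding is stated, slides carry only a study ID, the principal investigator has no access to medical records, and antibodies, dilutions and incubation steps are fixed for four proteins. The pilot prediction was reported as blinded. A reader might infer that nothing secures the reading; these passages show that to be wrong. They stand as partial safeguards, but none shows that a call is repeatable, and the form weakens the first.

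A reader might also infer that readings will be made unblinded, or that no image will ever be looked at twice. The documents do not say so. The second part of the form is completed after the laboratory analysis, so the first part may not have been consulted before the call. On repeat reading the documents are silent. What can be shown is an unreconciled conflict and the absence of a planned check.

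The illustration is open to fair criticism. The error rates have no documentary basis, the pilot values already contain whatever reading error occurred, and PPV at a set prevalence is not a planned analysis. No passage says that most relatives are unaffected. At 50% prevalence the loss is much smaller. The figures show possible size and are not evidence that errors occur.

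Finally, re-reading by the same person measures consistency only. A stable but wrong threshold would score well, and a reader who repeats the same mistakes would make agreement look better than the independent-error formula implies. Stored images also leave out sampling, staining and the choice of microscope field. All of this stands and limits what the fix may claim.

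**Conclusion.** The point holds in two parts. First, the synopsis claims accuracy and reproducibility for the main-study endpoint, and the design does not measure repeatability. Second, the claim of freedom from bias leans on blinding that section 6.1 and the DPIA describe incompatibly. The strong claim stands in the synopsis alone; section 14.2.1 says only that quantification may add bias and should not be read as repeating it.

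The size of any reading error is unknown. Under the assumed 2% to 10% random misreading, sensitivity would fall from 87.2% to between 85.7% and 79.7%, and specificity from 100% to between 98% and 90%. The effect on PPV depends heavily on the assumed prevalence. This does not invalidate the study. It should be corrected because the plan offers the untested property as the reason for its endpoint, and a check on stored images is feasible.

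**What to change.** 1. Delete the synopsis sentence and state instead: 'within-reader repeatability will be measured by coded re-reading; this does not test bias or accuracy'.
2. Have the same reader re-read the stored TIF images of a random 10% of participants (about 80), under new codes and without sight of the first call. Report agreement and kappa with 95% CIs beside sensitivity and specificity.
3. Reconcile section 6.1 with the DPIA by withholding the clinical part of the form from the reader until the call is locked.

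Cost: no new participants, samples or second reader; some reading time and one added table. With six smears each, 80 participants have up to 80 × 6 = 480 slides. The documents give no number of images per slide, so the hours cannot be stated. Withholding part of the form needs a change in how it is handled. The reported repeatability may prove less favourable than the sentence it replaces.

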If seen at the hospital, the study participants will just be asked to open their mouth. A study team member will rub a soft brush a few times at the inside of their cheek and smear the brush on a microscopy slide. The slide will be sprayed with 70% ethanol to preserve the material and taken to the research laboratory. The patient will have a total of 6 smears taken (3 from each cheek). For the majority of the patients, only a single sampling will be enough which will take place during one of their regular follow-up appointments at the cardiology clinic or using the at-home kit. There is no pain and no discomfort associated with the procedure and it lasts only a few seconds. In selected cases, however, if for instance we want to use the buccal smear to evaluate the effect of a change in medical treatment on protein distribution, the patient might be asked to provide the study team with another sample, again during one of his scheduled regular follow-up visits or using the same self-sampling kit at home. If the at-home kit is being used, the patient will be asked to obtain their own buccal smear samples using the materials provided and mail the slides back to City St George's, University of London.

Exfoliated buccal mucosa cells have been used as a source of material for various genetic tests and in studies of oral cancer but their use in studies of cardiovascular disease has been limited. Previous applications have included analysis of telomere length in buccal cells from patients with ischemic heart failure and measurements of intracellular magnesium levels in patients undergoing radiofrequency catheter ablation for atrial fibrillation. To the best of our knowledge, our study published at *Circulation Arrhythmia and Electrophysiology* 9(2) in 2016, was the first analysis of buccal mucosa cells in patients with a heritable form of heart disease.³ This analysis included 39 patients diagnosed with ACM, a primary myocardial disease characterized by an unusually high burden of arrhythmias and SCD as well as 15 carriers of disease-causing mutations without overt disease manifestation. In a subsequent analysis (unpublished data), 55 additional individuals affected by ACM were sampled and the positive predictive value of our approach in diagnosing the disease was 91.9%. Although highly arrhythmogenic, ACM is a

[figure not shown]

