Regardless of the outcome of the baseline analysis, all participants will be asked to provide the study team members with additional samples up to 3 times/year following their appointment, using a self-sampling kit, and then at their next regular follow-up appointment. If the interim results yielding from the analysis of the self-obtained samples, shows abnormal protein distribution, the medical providers may contact the participant and discuss with them the possibility of bringing their next regular appointment forward for discussion and further evaluation. Regarding the sub-study, the majority of participants will only be asked to provide buccal cells once. In selected cases we may invite them to provide an additional sample at their next regular appointment. Our buccal smear work has shown that one protein in particular, Connexin43, shows restored distribution in response to clinically effective anti-arrhythmic medication. Yet, to date, we do not know what is the mechanism of action through which drugs fix Connexin43 localization and hence restore normal cardiac rhythm. Our sub-study would show whether the drugs act by increasing protein production or merely shifting the protein to junctional sites facilitating electrical conduction.

Methods

Laboratory procedures (if applicable)

The samples obtained will be mailed to [name] research laboratory. The fixed slide will be dipped in blocking buffer (97 ml phosphate buffered saline (PBS), 3 ml normal goat serum, 1 gram of bovine serum albumin and 150 microliters of Triton-X for a total of 100ml). The slides shall be left to incubate for 45 minutes at room temperature. The primary antibody will then be added (I use a liquid-repellent pen to draw a circle around the area where the cells are) diluted in blocking

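### Cx43 restoration after a treatment change rests on one unconfirmed present/absent call before and one after, so between-occasion error alone can produce apparent restorations

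*Combined protocol and SAP*

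**What the plan says.** The synopsis, under Criteria for evaluation, sets the entry condition: "If a patient shows Cx43 remodeling during initial sampling", followed by a change of treatment decided by the care team. The follow-up is a single re-reading: "we would like to study Cx43 distribution again during one of his/hers follow up visits". The result is named but not defined: "If the new treatment plan results in restoration of Cx43 at the buccal mucosa cell connections". The synopsis then suggests that this could mark treatment success and later serve to judge therapy.

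Primary endpoints (14.2.1) allows only a present or absent result for each protein: "No quantification of immunoreactive signal will be performed as this approach may increase bias". On reliability the synopsis offers an assertion: "We deem that the qualitative approach is not subject to bias and will ensure accuracy and reproducibility of the results". The document gives no test-retest, between-reader or between-cheek agreement for Cx43 or any other protein.

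Two provisions could supply replication. Intervention plan and rationale (6.2) states: "The patient will have a total of 6 smears taken (3 from each cheek". Subsequent assessments (10.4) states that "all participants will be asked to provide the study team members with additional samples up to 3 times/year following their appointment". Neither is tied to a rule for classifying Cx43. Secondary endpoint analysis lists the effect of treatment changes on Cx43 as a planned use of the data but gives no method for it.

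**The concern.** Patients are selected because one call was abnormal and then judged by whether the same call becomes normal. Without quantification no minimum change can be required, so the cut-off for entry is also the cut-off for response. Anyone whose first or second call is wrong, or whose signal lies near the reader's threshold, can switch with no change in Cx43. Among patients selected as absent, the only switch that can be observed is towards present. When treatment does nothing, all such switches would be read as benefit.

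Two conclusions are at stake: whether Cx43 responds to treatment in the group, and whether a given patient can be described as restored.

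**Working it through.** **The plan's own figure.** Primary endpoint analysis reports plakoglobin absent in 34 of 39 ACM patients: 34/39 = 87.18%, printed as 87.1% (exact 95% CI 72.6% to 95.7%). The complement, 5/39 = 12.8%, is the only count in the document that resembles a miss rate. It concerns plakoglobin against clinical diagnosis, not Cx43 against a repeat reading, so it serves below only as one point in a range.

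**Model with no true change.** All error rates are assumptions, with errors independent between occasions.
- π = share of candidates whose Cx43 is truly remodelled (0.5 to 0.9)
- a = P(read present | truly remodelled), the miss rate
- b = P(read absent | truly normal), the false-absent rate

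One occasion before and one after:

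P(restored | entered) = [π(1−a)a + (1−π)b(1−b)] / [π(1−a) + (1−π)b]

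Two absent occasions before and two present occasions after:

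P = [π(1−a)²a² + (1−π)b²(1−b)²] / [π(1−a)² + (1−π)b²]

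**Worked cases, single calls.**
- a = b = 0.05, π = 0.5: (0.02375 + 0.02375) / 0.50 = 9.5%.
- a = 5/39, b = 0: π cancels and the result is a, or 12.8%.
- a = 5/39, b = 0.10, π = 0.5: (0.0559 + 0.0450) / 0.4859 = 20.8%.

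| Assumed errors | Single call each side | Two concordant calls each side |
|---|---|---|
| a = b = 0 | 0% | 0% |
| a = b = 2% | 2.2-3.9% | 0.04-0.08% |
| a = b = 5% | 5.5-9.5% | 0.3-0.5% |
| a = b = 10% | 11.0-18.0% | 1.1-2.0% |
| a = 12.8%, b = 0 | 12.8% | 1.6% |
| a = 12.8%, b = 5-10% | 13.3-20.8% | 1.7-2.7% |

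Ranges are over π = 0.5 to 0.9. With 20 selected patients (an assumed number), 12.8% means 20 × 0.128 = 2.6 false restorations expected. The chance of at least one is 1 − (34/39)^20 = 94%.

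**Failure to confirm at entry.** With no true change, the chance that a second pre-change call contradicts a first absent call is the same expression as the single-call formula. About 2-21% of first-abnormal patients would therefore fail to confirm.

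**Model with a large true effect.** Assume 80% of truly remodelled patients recover, with a = 5/39, b = 0.10, π = 0.9.
- Single-call entrants: 0.9 × 0.8718 + 0.1 × 0.10 = 0.7846 + 0.0100 = 0.7946. True restoration among them: 0.8 × 0.7846 / 0.7946 = 79.0%.
- Single-call observed: [0.7846 × (0.8 × 0.9 + 0.2 × 0.1282) + 0.01 × 0.9] / 0.7946 = 0.5940 / 0.7946 = 74.8%.
- Confirmed entrants: 0.9 × 0.8718² + 0.1 × 0.10² = 0.6840 + 0.0010 = 0.6850. True restoration among them: 0.8 × 0.6840 / 0.6850 = 79.9%.
- Confirmed observed: [0.6840 × (0.8 × 0.9² + 0.2 × 0.1282²) + 0.001 × 0.9²] / 0.6850 = 0.4463 / 0.6850 = 65.2%.

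The single-call figure is therefore too low here, and the confirmed figure lower still.

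**The case against.** Four stronger readings are tempting, and the documents support none of them.

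- **That one smear decides.** Each occasion yields six smears. They are shared among at least four antibodies (Laboratory procedures, 10.5.1), with no stated number of slides per protein and no rule for discordant slides. The accurate unit is one sampling occasion.
- **That the plan counts a patient as restored on one present call.** No restoration rule is written. The defect is the missing definition, together with a design that describes one re-reading.
- **That error can only inflate restoration.** This is exact when treatment does nothing. The last calculation shows the reverse under a large effect.
- **That 12.8% estimates the Cx43 error.** The five plakoglobin patients may read as present every time, in which case they would never switch. At 2% error the false share is only 2-4%.

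The selection step also rests on the synopsis alone. Secondary objectives (5.2) and section 6.2 do not require baseline remodelling. Section 10.4 resamples everyone, so switches from present to absent could be seen in the wider cohort. Finally, the synopsis calls this a potential outcome and hedges its interpretation, and Secondary endpoints (14.2.2) says none apply.

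These arguments limit the size and weight of the point. They do not supply a definition, a confirmation rule or a repeatability figure.

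**Conclusion.** The point stands as a minor one. As written, an apparent Cx43 restoration cannot be told apart from between-occasion error. With no treatment effect, single calls would show restoration in about 2-21% of selected patients for assumed miss rates of 2-12.8%. Two concordant calls on each side bring this below 3%. The figures rest on independent errors and 50-90% truly remodelled, and within-patient stability of errors would lower them. Confirmation is not a complete answer, because it can under-count true restorations: 65% against a true 79-80% in the example. Both proportions are therefore needed, along with a direct measure of spontaneous switching.

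**What to change.** In the synopsis (Criteria for evaluation) and Secondary endpoint analysis:

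1. Define remodelled and restored per sampling occasion, including how many slides are stained for Cx43 and how discordant slides are resolved.
2. From the repeat sets requested in 10.4, report (a) the single-call restored proportion and (b) the confirmed proportion: absent on the last two sets before the change and present on two consecutive sets after it. Label patients with only one set on either side as unconfirmed.
3. From the same sets, report how often the Cx43 call switches in remodelled patients with no treatment change, as the benchmark for (a).
4. Describe an individual as restored only on confirmed calls.
5. Do not count slides from the two cheeks at one occasion as confirmation, since they do not test between-occasion noise.

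Sections 6.2 and 10.3 say that one sampling is enough for most patients, whereas 10.4 asks everyone for repeats. These must be reconciled, because the fix depends on the repeat sets.

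The change needs protocol and SAP wording and uses samples already requested. Its costs are fewer evaluable patients (about 2-21% of first-abnormal patients failing to confirm at entry in the binary model, plus those with too few sets), later classification, and the under-counting shown above when false absent calls are common. No treatment decision is affected.
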